5.3.2.3. Prior and Concomitant Medications

Incomplete prior/concomitant medication dates will be imputed as follows:

- If the medication date is missing completely, no imputation will be performed.
- If the day of medication date is missing, then the medication date will be replaced by 1st of the month. For example, if the medication start date is --/JAN/2015, then the imputed medication start date will be 01/JAN/2015.
- If both the day and month of medication start date are missing, then the medication date will be replaced by January 1st of the year. For example, if the medication start date is --/---/2014, then the imputed medication start date will be 01/JAN/2014.
- In all other cases the missing medication day or missing medication month will be replaced by 1.

- Incomplete stop date will be replaced by the last day of the month (if day is missing).
- Incomplete stop date will be replaced by the last month of the year (if month is missing).
- In all other cases the incomplete medication stop date will not be imputed.

5.3.2.4. Exposure

No imputation will be done for first dose date or last dose date.

5.3.3. Imputation Rules for Date of Last Contact and Efficacy Assessments

5.3.3.1. Date of Last Contact

The date of last contact will be derived for patients not known to have died at the analysis cut-off using the latest complete date among the following:

- All patient assessment dates (blood draws (laboratory, PK), vital signs, performance status, ECG, tumor assessments).
- Start and end dates of anti-cancer therapies administered after study treatment discontinuation.
- AE start and end dates.
- Study drug start and end dates.
- Date of discontinuation on disposition eCRF pages (do not use if reason for discontinuation is lost to follow-up).

Only dates associated with actual examinations of the patient will be used in the derivation. Dates associated with a technical operation unrelated to patient status such as the date a blood sample was processed will not be used. Assessment dates after the cut-off date will not be applied to derive the last contact date.

5.3.3.2. Death Date

Partial death dates will be imputed based on the last contact date:

- If the day or both the day and the month is missing, death will be imputed to the maximum of the full (non-imputed) day after the date of last contact and the following:
 - Missing day: 1st day of the month and year of death.
 - Missing day and month: January 1st of the year of death.

5.3.3.3. Tumor Assessments

All investigation dates (eg, X-ray, CT scan) must be completed with day, month and year.

If there are multiple scan dates associated with an evaluation, ie, radiological assessments occur over a series of days rather than the same day, the choice of date of assessment could impact the date of progression and/or date of response. If there are multiple scan dates associated with an evaluation, the earliest of the scan dates associated with the evaluation will be used as the date of assessment.

If one or more investigation dates for an evaluation are incomplete but other investigation dates are available, the incomplete date(s) are not considered for calculation of the assessment date and assessment date is calculated as the earliest of all investigation dates (eg, X-ray, CT-scan).

If all measurement dates for an evaluation have no day recorded, the 1st of the month is used.

If the month is not completed, for any of the investigations for an evaluation, the respective assessment will be considered to be at the date which is exactly between the previous and the following assessment. If both a previous and following assessments are not available, this assessment will not be used for any calculations.

5.3.3.4. Date of Start of New Anti-cancer Therapy

Incomplete dates for start date of new anti-cancer therapy (drug therapy, radiation, surgery) will be imputed as follows and will be used for determining censoring dates for efficacy analyses and in the derivation of the end of on-treatment period.

- If the end date of new anti-cancer therapy is:
 - completely missing then it will be ignored in the imputations below.
 - partially missing with only year (YYYY) available then the imputations below will consider 31DECYYYY as the end date of the new anti-cancer therapy.
 - partially missing with only month and year available then the imputations below will consider the last day of the month for MMMYYYY as the end date of the new anti-cancer therapy.
- If the start date of new anti-cancer therapy is completely or partially missing then the imputed start date of new anti-cancer therapy is:
 - completely missing then it will be ignored in the imputations below.
 - partially missing with only year (YYYY) available then the imputations below will consider 01JANYYYY as the start date of the new anti-cancer therapy.

- partially missing with only month and year available then the imputations below will consider the first day of the month for MMMYYYY as the start date of the new anti-cancer therapy.

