5.2.5. Definition of Start of New Anti-cancer Drug Therapy

Start date of new anti-cancer drug therapy is used to determine the end of the on-treatment period (see [Section 5.2.7](#)).

The start date of new anti-cancer drug therapy is the earliest start date of anti-cancer drug therapy recorded in the 'Follow-up Systemic Therapy – for Cancer' eCRF pages that is after the first dose of study treatment. When start date of anti-cancer drug therapy is missing or partially missing, the imputation rules described in [Section 5.3.3.4](#) should be applied using only data from the 'Follow-up Systemic Therapy – for Cancer' eCRF pages.

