5.2.6. Definition of Start of New Anti-cancer Therapy

Start date of new anti-cancer therapy (drug, radiation, surgery) is used for censoring in efficacy analyses (see [Section 6.2.2](#)).

The start date of new anti-cancer therapy is the earliest date after the first dose of study treatment amongst the following:

- Start date of anti-cancer drug therapy recorded in the ‘Follow-up Systemic Therapy – for Cancer’ eCRF pages.
- Start date of radiation therapy as identified by clinical review based on data recorded in the ‘Concomitant Radiation Therapy’ eCRF page. The following cases will not be considered as new anti-cancer therapy: ‘Type of Radiation Therapy’ = ‘Palliative’ and radiotherapy to a non-target tumor lesion.
- Surgery date recorded in ‘Concomitant Surgery’ when “Surgery Outcome” = ‘Resected’ or ‘Partially Resected’.

When start date of anti-cancer therapy is missing or partially missing, the imputation rules described in [Section 5.3.3.4](#) should be applied.

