5.2.7. Definition of On-treatment Period

Safety endpoints will be summarized based on the on-treatment period unless otherwise specified.

On-treatment period is defined as the time from the first dose of study treatment through minimum (30 days + last dose of study treatment, start day of new anti-cancer drug therapy – 1 day).

Safety data collected outside the on-treatment period as described above will be listed and flagged in listings but not summarized.

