6.2.2.1. Objective Response as Assessed by the Investigator per RECIST v1.1

The following analyses will be based on the FAS by treatment group. Assessment of response will be made using RECIST v1.1.

Best Overall Response (BOR) will be assessed based on reported overall lesion responses at different evaluation time points from the first dose of study treatment until the first documentation of PD, according to the following rules:

- CR = at least two determinations of CR at least 4 weeks apart and before first documentation of PD.
- PR = at least two determinations of PR or better at least 4 weeks apart and before first documentation of PD (and not qualifying for a CR).
- SD (applicable only to patients with measurable disease at baseline) = at least one SD assessment (or better) ≥ 6 weeks after the first dose of study treatment and before first documentation of PD (and not qualifying for CR or PR).
- Non-CR/non-PD (applicable only to patients with non-measurable disease at baseline) = at least one non-CR/non-PD assessment (or better) ≥ 6 weeks after the first dose of study treatment and before first documentation of PD (and not qualifying for CR or PR).

- PD = progression \leq 12 weeks after the first dose of study treatment (and not qualifying for CR, PR, SD or non-CR/non-PD).
- NE: all other cases.

Only tumor assessments performed on or before the start of any further anti-cancer therapies will be considered in the assessment of BOR. Clinical deterioration will not be considered as documentation of disease progression.

Objective Response (OR) is defined as BOR of CR or PR according to RECIST v1.1

Patients who do not have a post-baseline radiographic tumor assessment (including due to early clinical progression), who receive anti-cancer therapies other than the study treatments prior to reaching a CR or PR, or who die, progress, or drop out for any reason prior to reaching a CR or PR will be counted as non-responders in the assessment of OR. Each patient will have an objective response status (0: no OR; 1: OR). OR rate (ORR) is the proportion of patients with OR in the analysis set.

ORR by treatment group will also be calculated along with the 2-sided 95% CI using the Clopper-Pearson method (exact CI for a binomial proportion as computed by default by the FREQ procedure using the EXACT option).

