In addition, the frequency (number and percentage) of patients with BOR of CR, PR, SD, non-CR/non-PD (applicable only to patients with non-measurable disease at baseline), PD and NE will be tabulated. Patients with BOR of NE will be summarized by reason for having NE status. The following reasons will be used:

- Inadequate baseline assessment (includes missing assessment or non-measurable disease at baseline).
- No post-baseline assessments due to death.
- No post-baseline assessments due to other reasons.
- All post-baseline assessments have overall response NE.
- New anti-cancer therapy started before first post-baseline assessment.
- SD of insufficient duration (<6 weeks after the first dose of study treatment).
- PD too late (>12 weeks after the first dose of study treatment).

Special and rare cases where BOR is NE due to both early SD and late PD will be classified as 'SD too early'.

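### SAP 5.3.3.4 can impute the start of a new systemic therapy before the last study dose: its final step is missing and nothing floors the date at last dose

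*SAP*

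**What the plan says.** SAP 5.3.3.4 covers incomplete dates of new drug therapy, radiation and surgery. It says the result drives both efficacy censoring and the end of the on-treatment period. For a year-only start: "partially missing with only year (YYYY) available then the imputations below will consider 01JANYYYY as the start date of the new anti-cancer therapy". A month-and-year start becomes the first of that month. The section also builds an end date; for a year-only end, "the imputations below will consider 31DECYYYY as the end date of the new anti-cancer therapy". Six bullets point to imputations that should follow: four supply a value, and two say that a completely missing date is ignored. The section then stops and Section 6 begins, with no redaction or missing-figure mark. The end date is used nowhere.

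The only other bound is the first dose. SAP 5.2.5 takes the earliest systemic-therapy start on the follow-up "eCRF pages that is after the first dose of study treatment". SAP 5.2.6 reads "The start date of new anti-cancer therapy is the earliest date after the first dose of study treatment amongst the following".

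The on-treatment period (SAP 3.5.1, 5.2.7) ends 30 days after the last dose or, if earlier, the day before new drug therapy. "Safety data collected outside the on-treatment period as described above will be listed and flagged in listings but not summarized". For best overall response, SAP 6.2.2.1 says "Only tumor assessments performed on or before the start of any further anti-cancer therapies will be considered in the assessment of BOR".

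A partial death date does have a floor in SAP 5.3.3.2: "death will be imputed to the maximum of the full (non-imputed) day after the date of last contact" and the first day of the recorded period.

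**The concern.** On one reading, 1 January or the first of the month is only an input to a step that was never written, and two programmers could finish it differently. On the other, it is the final value and can fall while the patient is still receiving study drug. Protocol 5.7.1 prohibits other systemic anti-cancer therapy during treatment and the source is a follow-up page, so such a date would usually be an artefact of the imputation.

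Adverse events, laboratory values and ECGs after the artefact date would drop out of the summaries. Later scans would leave BOR and irBOR, and expansion-cohort PFS and DR events would become censored. irPFS and irDR are more exposed: Table 6 censors at new therapy before confirmed irPD, so the confirming scan must also precede the imputed date. Dose-finding cohorts hold 3 to 9 patients evaluable for MTD (Protocol 3.1.9), so one patient's missing event moves an adverse-event percentage by 1/9 to 1/3, or 11 to 33 points.

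**Working it through.** The plan gives no figure for this rule, so I applied it by date arithmetic. All dates, gaps and durations below are assumptions.

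**Rule.** F = first dose, L = last dose, S = imputed start. If S is after F, the window ends at min(L + 30 days, S − 1 day). If S is on or before F, I take the therapy as dropped and the window as ending at L + 30. The SAP does not say whether the first-dose condition is tested before or after imputation; I assume after.

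**Example.** F = 10 Nov 2015, L = 20 Jun 2016, therapy start recorded as 2016.
- S = 1 Jan 2016, which is after F and so is accepted.
- The window ends at min(20 Jul 2016, 31 Dec 2015) = 31 Dec 2015. That keeps 21 + 31 = 52 of 224 days; 224 − 52 = 172 on-drug days and up to 30 follow-up days leave the summaries.
- Eight-weekly scans fall on 5 Jan, 1 Mar, 26 Apr and 21 Jun 2016, all after S. BOR becomes NE, with the reason "New anti-cancer therapy started before first post-baseline assessment".
- For an expansion patient with PD on 21 Jun, PFS of (224 + 1)/30.4375 = 7.39 months becomes a censored (0 + 1)/30.4375 = 0.03 months.

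This is close to a worst case, since the first scan misses by four days.

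**Frequency, given a partial date.** I took every last-dose date in 2015–2016 (731 dates) and a true start 7, 14, 28 or 56 days later. Where four values are shown, they follow that order.

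| Days, first to last dose | Year-only S between first and last dose | Median on-drug days removed | S on or before first dose (dropped) |
|---|---|---|---|
| 84 | 23.0% | 42.5 | 75.1 / 73.2 / 69.4 / 61.7% |
| 112 | 30.6% | 56.5 | 67.4 / 65.5 / 61.7 / 54.0% |
| 168 | 46.0% | 84.5 | 52.1 / 50.2 / 46.4 / 38.7% |
| 364 | 98.1 / 96.2 / 92.3 / 84.7% | 180 / 176 / 169 / 155 | 0% |

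A month-only date falls on or before the last dose in 77.0, 54.0, 8.1 and 0.0% of cases. It removes a median of 12, 9 and 2 on-drug days (maximum 24, 17 and 3) at the first three gaps.

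**Floor at the day after last dose.** When the floor sets the date, the window ends at L. With a gap of g days the true window runs min(30, g − 1) days past L, so 6, 13, 27 or 30 days are lost. When the current rule drops the therapy, the window is instead max(0, 31 − g) = 24, 17, 3 or 0 days too long. Year-only comparison at 84 days of dosing:
- 28-day gap: mean absolute window error 19.1 days now, 26.0 with the floor.
- 56-day gap: 17.9 now, 26.7 with the floor.
- At these gaps 69% and 62% of windows get worse and 23% improve.

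At 112 days, 62% and 54% get worse and 31% improve, with mean error slightly lower. The floor helps at gaps of 7 and 14 days and at 364 days of dosing.

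**Checks of the floor and cap.**
- In the example, S becomes 21 Jun 2016, the window ends 20 Jun and all 224 days are kept. The three earlier scans return. The 21 Jun scan falls on S itself, so BOR keeps it (on or before) and irBOR does not (before).
- MAR2016 with last dose 20 Jun 2016: the cap gives 31 Mar 2016, so a recorded on-treatment start stays visible as a deviation.

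**The case against.** The case for leaving this alone is partly right. The number of partial dates is unknown, and Protocol 6.3 asks for the therapy start date on the CRF for patients in disease follow-up, so they may be few. Efficacy is descriptive, PFS and DR apply to expansion cohorts only, and the excluded safety data stay listed and flagged. It also stands that the floor worsens many safety windows when dosing is short and the gap is 28 days or more. None of this answers the main point: followed as written, the rule can remove on-drug data.

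Four stronger readings are tempting, and the documents do not support them.
- **MTD is at risk.** The DLT analysis does not use this date. Nor do the death tables, which count from the last dose.
- **Dropped therapies are harmless because data collection stops at new therapy.** Protocol 8.2 ends only nonserious AE reporting there. SAEs are collected for 60 days after the last dose, and deaths in that period are reported whatever treatment intervenes. A dropped therapy can let SAEs into the summaries and turn a censored PFS time into a death event.
- **The efficacy date should also be floored at the last scan.** Protocol 6.3 stops data collection only for patients in disease follow-up. An EOT scan at 28 (+7) days after last dose (Protocol 6.2) may follow new therapy. Assumed example: last dose 25 May 2016, true start 5 Jun recorded as JUN2016, PD on an EOT scan of 24 Jun. The last-dose floor leaves S at 1 Jun and the patient censored, as Table 3 intends. A last-scan floor moves S to 25 Jun and counts the post-therapy PD as an event.
- **All six references feed values forward.** Only four do.

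**Conclusion.** The concern holds as a flaw in a stated rule. SAP 5.3.3.4 is unfinished, and its only start value can place a prohibited systemic therapy before the last study dose. Where that happens with a year-only date, the median loss is about 43 to 85 on-drug days for 84 to 168 days of dosing, and 155 to 180 for 364 days. Month-only dates cost at most 24 on-drug days at the gaps examined. These sizes depend on a partial date being present, on assumed gaps of 7 to 56 days and evenly spread last-dose dates, and on testing the first-dose condition after imputation. The effect is confined to safety summaries and to the RECIST and irRECIST efficacy endpoints. It should be corrected before database lock but does not touch the primary endpoint.

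**What to change.** Complete SAP 5.3.3.4 for systemic drug therapy with a partial start date:

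*Imputed start = the later of (a) the first day of the recorded month or year and (b) the day after the last dose of study treatment, capped at the earlier of the last day of the recorded month or year and the (imputed) end date of that therapy. The requirement that the date follow the first dose is applied after this floor and cap.*

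Add no floor at the last tumor assessment. Do not apply the last-dose floor to radiotherapy or surgery. Leave completely missing dates as now. Report the number of patients with a floored date.

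State the downside in the SAP. When (b) sets the date, the window ends at the last dose and up to 30 days of post-dose safety data are listed but not summarized. For year-only dates with short treatment and a gap of 28 days or more, that can exceed the error the current rule makes when it drops the therapy. A scan taken after the floored date but before the true start also stays out of the efficacy analyses. In exchange, the much larger loss of on-drug time is removed. The change is one SAP paragraph and a small programming edit, with no new data.

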6. ANALYSES AND SUMMARIES

Refer to [Section 4](#) for definitions of analysis sets and [Section 5.2](#) for general methodology.

6.1. Primary Endpoints

6.1.1. DLT

6.1.1.1. Primary Analysis

The primary analyses will be based on the DLT-evaluable set. DLTs will be listed and summarized by treatment group.

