2.1. Study Objectives

Primary Objectives

- To estimate the Maximum Tolerated Dose (MTD) and select the Recommended Phase 2 Dose (RP2D) of PF-05082566 in combination with mogamulizumab in patients with advanced solid tumors.

Secondary Objectives

- To evaluate the overall safety profile;

- To characterize the pharmacokinetics (PK) of PF-05082566 and mogamulizumab when given in combination;
- To evaluate the immunogenicity of PF-05082566 and mogamulizumab when given in combination;
- To document any anti-tumor activity.

CCI [REDACTED]

- CCI [REDACTED]
[REDACTED]

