4.3. Other Analysis Set

4.3.1. DLT-evaluable Set

[figure not shown]
The DLT-evaluable set includes all enrolled patients who are eligible for the study and receive study treatment. Note that every patient will contribute to the determination of the MTD including patients who are lost to follow-up prior to completion of the 2 cycles' DLT observation period.

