5.2. General Methods

As described in [Section 3.4](#), in this study ‘**treatment group**’ refers to one of the following:

- Dose Level -1: PF-05082566 1.2 mg/kg q4wks + mogamulizumab 0.5 mg/kg;
- Dose Level 1: PF-05082566 1.2 mg/kg q4wks + mogamulizumab 1 mg/kg;
- Dose Level 1a: PF-05082566 100 mg q4wks + mogamulizumab 1 mg/kg;
- Dose Level 2: PF-05082566 2.4 mg/kg q4wks + mogamulizumab 1 mg/kg;
- Dose Level 3: PF-05082566 5 mg/kg q4wks + mogamulizumab 1 mg/kg.

Baseline characteristics, disposition and efficacy data will be summarized based on the FAS by treatment group.

DLTs will be summarized based on the DLT-evaluable set by treatment group.

Other safety data, exposure data, concomitant medications and non-drug treatments will be summarized based on the safety analysis set by treatment group.

PK data will be summarized based on the PK analysis sets by treatment group.

CCI

Immunogenicity data will be summarized based on the immunogenicity analysis set by treatment group.

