5.2.3. Presentation of Continuous and Qualitative Variables

Continuous variables will be summarized using descriptive statistics ie, number of non-missing values, mean, median, standard deviation (SD), minimum, maximum and first and third quartile (Q1 and Q3).

Qualitative variables will be summarized by frequency counts and percentages. Unless otherwise specified, the calculation of proportions will include the missing category. Therefore counts of missing observations will be included in the denominator and presented as a separate category.

In case the analysis refers only to certain visits, percentages will be based on the number of patients still present in the study at that visit, unless otherwise specified.

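### SAP 6.1.1.1 reports only an unweighted DLT summary, which runs low if DLT-free patients leave before week 8, and Section 6 never reports the final TITE-CRM fit on which the MTD is defined.

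*SAP*

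**What the plan says.** The first part of the primary objective in SAP Section 2.1 is "To estimate the Maximum Tolerated Dose (MTD) and select the Recommended Phase 2 Dose (RP2D) of PF-05082566". Protocol Sections 3.1.9 and 3.3 define the MTD as the highest combination dose whose DLT rate, as estimated by the model, is below 30%. SAP Section 5.1.2 specifies the model: a power function, a normal prior on one parameter, the posterior mean, and weights for patients with part of the 8-week window completed. It does so as rules for assigning doses.

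The primary analysis itself, SAP Section 6.1.1.1, says: "The primary analyses will be based on the DLT-evaluable set. DLTs will be listed and summarized by treatment group". Section 5.2 repeats it: "DLTs will be summarized based on the DLT-evaluable set by treatment group".

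Two other sections determine what such a summary contains.

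- SAP Section 4.3.1 defines the set: "The DLT-evaluable set includes all enrolled patients who are eligible for the study and receive study treatment". It adds that "every patient will contribute to the determination of the MTD including patients who are lost to follow-up prior to completion" of the two-cycle window. No minimum follow-up is required.
- SAP Section 5.2.3 gives the general rule: "Qualitative variables will be summarized by frequency counts and percentages". Unless otherwise specified, "counts of missing observations will be included in the denominator and presented as a separate category".

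Protocol Section 9.6.1 asks for a listing of DLTs per dose level and refers MTD estimation back to the study design section. SAP Section 6 plans no output for the final posterior DLT rates, their intervals or the MTD.

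**The concern.** The quantity that answers the primary objective is a weighted model estimate. The quantity planned for the primary table is an unweighted count and, by Section 5.2.3, a percentage. They treat incomplete follow-up differently. The model gives a DLT-free patient who leaves at week 2 an initial weight of 2/8. The summary leaves that patient in the denominator as a whole person.

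They are also organised differently. Protocol Section 3.1.9 pools the 100 mg flat dose (Level 1a) with 1.2 mg/kg (Level 1) in the model, whereas the SAP treatment groups keep them apart.

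Finally, SAP Sections 6.2.2.1, 6.2.2.3 and 6.2.2.5 attach 95% confidence intervals to response rate, duration of response and PFS, all secondary, while the primary result has no measure of uncertainty. A reader of the final report could see a DLT percentage well below 30% at a dose that the model placed above it, with nothing in the planned outputs to explain the difference.

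**Working it through.** **The plan's own figures.** The documents state no DLT-rate estimate. The related figures reproduce: 1 − 0.95^30 = 0.785 (stated 0.79), 1 − 0.90^30 = 0.958 (stated 0.96), and the prior interval exp(±1.65) = [0.19, 5.21].

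**Step 1: expected size of the understatement.** Inputs: true DLT rate p = 0.30, the MTD limit; early dropout d, not given in the documents, so assumed from 0 to 30%. If DLT and dropout times are independent and uniform over 8 weeks, a dropout hides half of the DLTs that would have occurred, so the expected crude rate is p(1 − d/2). If all dropouts leave at the start, it is p(1 − d).

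| Dropout d | 0% | 10% | 20% | 30% |
|---|---|---|---|---|
| p(1 − d/2) | 30.0% | 28.5% | 27.0% | 25.5% |
| p(1 − d) | 30% | 27% | 24% | 21% |

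At 20% dropout with uniform times, a true rate of 0.30/0.90 = 33.3% shows as 30%.

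**Step 2: crude and weighted denominators in one cohort.** Assume nine patients and two DLTs. The crude rate is 2/9 = 22.2% however long the others were followed. With linear weights:

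- no losses: 2/9 = 22.2%
- two lost at week 4: 2/(7 + 2 × 0.5) = 2/8 = 25.0%
- two lost at week 2: 2/(7 + 2 × 0.25) = 2/7.5 = 26.7%
- three lost at week 2: 2/(6 + 3 × 0.25) = 2/6.75 = 29.6%
- three lost at week 1: 2/(6 + 3 × 0.125) = 2/6.375 = 31.4%

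**Step 3: the model itself.** The likelihood is F for a DLT and 1 − wF for none, with F_i = p_i^exp(β), prior N(0, 1), and the illustrative p_i of 0.095, 0.186, 0.300 and 0.422 from SAP Section 5.1.2. I assumed that these belong to Levels −1, 1/1a, 2 and 3, and assumed data of 1/9, 1/6 and 2/9 DLTs at Levels 1, 2 and 3.

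| | Crude, Level 3 | Model, Level 3 | 90% credible interval | Pr(rate >30%) |
|---|---|---|---|---|
| Full follow-up | 22.2% | 28.7% | 15% to 44% | 0.44 |
| Three DLT-free Level 3 patients lost at week 2 | 22.2% | 31.9% | 17% to 48% | 0.57 |

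The model estimate crosses 30% and the crude figure does not move. If Levels 1, 2 and 3 take the first three p_i instead, the Level 3 estimate goes from 28.0% to 31.1%, the same crossing.

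**Step 4: no losses at all.** With full follow-up the data above give 11.1%, 16.7% and 22.2% crude, against 8.8%, 17.5% and 28.7% from the model. With 1/9, 2/6 and 2/9 the crude rates are not even monotone (11.1%, 33.3%, 22.2%), while the model gives 11.9%, 21.8% and 33.6%. This gap is not bias. It is the difference between separate proportions and a one-parameter curve.

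**Step 5: would a DLT-or-complete rate be better?** At p = 0.30 and d = 20% with uniform times, observed DLTs are 0.30 × 0.90 = 0.27 and DLT-free completers 0.70 × 0.80 = 0.56. The rate is 0.27/(0.27 + 0.56) = 32.5%, which is 2.5 points high, against 3.0 points low for the crude rate. It is not a clean replacement.

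**The case against.** The strongest reply is that the MTD is not read from this table. SAP Section 5.1.2 contains the full model, Protocol Section 9.6.1 sends MTD estimation to the design section, and the listing in SAP 6.1.1.1 matches what the protocol asks for. That stands. A reader might infer that the SAP replaces the model with a crude rate, or that dose selection rests on the crude rate. The documents do not support either reading; the gap is in what is reported as the primary result.

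Other parts of the reply also stand.

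- SAP 6.1.1.1 names no percentage. That comes from Section 5.2.3, which would show missing DLT status as its own category. The SAP does not say whether an incomplete window counts as missing, so it cannot be asserted that early leavers are coded DLT-free. In both cases they stay in the denominator and lower the percentage.
- The denominator is eligible treated patients, not every treated patient.
- Low bias is not inevitable. It needs DLT-free losses before week 8. The cut-off in SAP Section 2, 24 months after the last patient's first dose, means that nobody still under observation is inside the window. Stopping treatment is not itself a loss, since adverse events are generally followed for 28 days after the last dose unless new anticancer therapy starts.
- The split of Levels 1 and 1a is not irreconcilable with the model: the two rows can be added.

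One could also say that intervals are optional in a study without hypothesis tests. But an interval describes the precision of an estimate and needs no test, and this SAP already gives intervals for secondary endpoints.

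**Conclusion.** The point holds as a reporting and analysis gap that should be corrected. The planned primary output is not the estimate on which the MTD is defined, and it carries no uncertainty. Its percentage understates the DLT rate when DLT-free patients leave before week 8. The plan foresees such losses: Section 4.3.1 keeps these patients in the set, and Section 5.1.2 cites drop-out as one reason for choosing TITE-CRM.

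The understatement at a true rate of 30% is 1.5 to 4.5 points for assumed dropout of 10% to 30% at uniform times, up to 9 points if 30% leave at the start, and zero without early dropout. The example in which Level 3 crosses 30% rests on assumed DLT counts, the illustrative prior rates, an assumed mapping of those rates to dose levels, and linear weights; the SAP provides for an adaptive cyclical weight function, which would change the figures. The absence of a final fit from Section 6 depends on none of these assumptions.

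**What to change.** Amend SAP Section 6.1.1.1 so that the primary output is the final TITE-CRM fit on the DLT-evaluable set, using the final weights. Report the posterior DLT probability and credible interval for each dose level, with Levels 1 and 1a pooled as in the model, and the MTD that follows.

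Keep the crude DLT counts by treatment group as supportive. Beside them show the number who completed the 8-week window and the number incompletely followed, and say how an incomplete window is coded. If a rate among patients with a DLT or a complete window is also shown, state that it is biased upward.

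The cost is one SAP paragraph and one table, from a model already needed for dose allocation. The reported DLT rate may look slightly less favourable than the crude one.
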